2.4 Further Exploratory Study Endpoints

- Quality of life measures (see attachments)
 - St. Louis University Mental Status Exam (SLUMS)
 - EORTC Quality of Life Questionnaire C-30
 - EORTC Quality of Life Questionnaire BN-20
- Serum markers for tissue apoptosis and for neuronal damage

Several different quality-of-life measures following radiation treatment of the brain have been validated in large-scale studies internationally. We will use the EORTC Quality of Life Questionnaire-Core 30/Brain Cancer Module-20 (EORTC QLQ-C30/BN20), which has been employed in several RTOG and EORTC studies. (See Attachment 1.) As discussed in RTOG-0825 protocol documentation:

"The EORTC QLQ C-30/BN-20 were developed and validated for use in this [brain cancer] patient population. The QLQ C-30 is a 30-item self-report questionnaire that has patients rate the items on a 4-point scale, with 1 "not at all" to 4 "very much." The instrument measures several domains, including physical functioning, role functioning, emotional functioning, cognitive functioning, social functioning, fatigue, pain, nausea and vomiting, and several single items (dyspnea, insomnia, anorexia, constipation,

diarrhea, and financial impact). The BN-20 consists of 4 scales comprised of multiple items (future uncertainty, visual disorder, motor dysfunction, communication deficit) and 7 single items (headache, seizures, drowsiness, hair loss, itching, difficulty with bladder control, and weakness of both legs). The combined instrument takes an average of 8 minutes to complete by patients with primary brain tumors [24].”

Several mental status examinations have been used in the literature, with the Mini-Mental State Exam (MMSE), dating back more than 30 years, being the most popular. However, the St. Louis University Mental Status (SLUMS) examination has been shown to be more sensitive than the MMSE for detecting mild dementia [25], and it is free for academic research use, while the MMSE requires a fee. Hence, we are employing the SLUMS exam in this study.

Serum markers for brain metastases responding to radiation treatment have not been demonstrated to date, nor have serum markers for radiation damage to normal brain tissue been documented. In this protocol we test two potential markers: S100 β and NSE. Exploratory tests of serum markers will be performed following SRS-HBO using these markers found to be specific for neuronal damage.

Apoptosis after SRS has been shown to arise 6 hours after the procedure, to continue up to 48 hours, but to decline by 72 hours post-SRS [26]. S100 β and NSE are relatively specific for neurological injury and have been shown to be potentially useful serum markers of early hypoxic brain injury [27]. We hypothesize that these will be elevated following SRS (due to damage of normal brain tissue adjacent to tumor targets). We propose to test S100 β and NSE levels 24-48 hours after the SRS treatment in a subgroup of patients who have separately consented to this portion of the study. We anticipate that such preliminary data may be of interest in their own right, and that they may also be useful for further analysis should a larger study be pursued subsequently of SRS and HBO treatments for patients with malignant brain lesions.

3 Subject Selection and Withdrawal

3.1 Inclusion Criteria

Patients meeting all the following criteria are eligible for this trial:

- Metastatic brain tumor referred to radiation oncology for treatment
- Size of the presenting metastatic lesion up to 5.0 cm diameter
- Age \geq 18 years
- Patients must give informed consent indicating they are aware of the investigational nature of this treatment
- Karnofsky Performance Status \geq 70% (Zubrod score 0 to 1)
- Women of childbearing potential must have a negative serum or urine pregnancy test within 14 days to start of study therapy
- CBC and CMP within 30 days to start of study therapy

- Chest imaging (Chest Xray or Chest CT) within past 12 months, that does not show any contraindication to hyperbaric therapy (if patient has had any thoracic surgery or other significant event that might have affected the thorax such as trauma, pneumothorax, chest tube insertion, pleurodesis, or thoracentesis and has not had imaging since that event, then the imaging should be repeated).
- Neurosurgery Consult

3.2 Exclusion Criteria

Patients with the following conditions are not eligible to participate in this trial:

- Pregnant women or women of childbearing potential without adequate contraception. Contraception, which can include abstinence, is required since the last menstrual period until completion of SRS.
- Evidence of pneumothorax
 - Untreated pneumothorax risks tension pneumothorax during ascent in HBO chamber
- COPD with CO₂ retention
 - Such patients can develop respiratory depression as HBO reduces their hypoxic drive
- Uncontrolled seizure disorder
 - Note that patients on adequate antiepileptic medications may receive HBO
- Claustrophobia resistant to medication
 - Pre-medication with anxiolytics is generally sufficient for almost all anxious patients undergoing HBO treatment
- History of middle ear surgery
 - Failure to equalize pressure in the middle ear can cause displacement of middle ear structures with consequent hearing loss
 - To clarify: placement of a tympanostomy tube is not a contraindication to HBO, and in fact may improve tolerability of the procedure
- History of bleomycin administration
 - HBO can exacerbate interstitial pneumonitis in such patients
- Current cis-platinum chemotherapy (i.e. therapeutic levels in the bloodstream at the time of HBO therapy)
 - HBO can increase cytotoxicity of cis-platinum
- Uncontrolled high blood pressure
 - HBO can increase systemic vascular resistance
- Unstable angina or myocardial infarction within the previous 3 months
 - Increased afterload due to HBO can increase myocardial workload
- Cardiac EF ≤ 35%
 - Pulmonary edema can arise with HBO in certain patients with severe heart failure
 - In patients with prior history of CHF, subsequent echocardiogram and ECG are required to establish EF>35%
- Treatment with disulfiram

- Disulfiram inhibits superoxide dismutase and is not approved for use concomitantly with hyperbaric oxygen therapy
- Active drug/alcohol dependence or abuse
- Lack of adequate social support structures, e.g. homelessness
- Tumors with potential confounding results on serum marker studies
 - Small cell (neuroendocrine) carcinomas
 - Carcinoid tumors

3.3 *Subject Recruitment and Screening*

Subjects will be recruited from patients who are potential candidates for SRS treatment at DHMC for brain metastases. Such patients are referred to radiation oncology by practitioners at DHMC and by physicians at outlying hospitals.

The patient's first visit with radiation oncology will serve to screen the patient for most of the inclusion and exclusion criteria noted above. If the patient appears to be a candidate and wishes to enroll on the protocol, then he/she will be scheduled for a visit with the hyperbaric medicine service. At this visit the subject will be screened for any contraindications to hyperbaric oxygen therapy, and will be given a chance to visit the chamber.

3.4 *Early Withdrawal of Subjects*

3.4.1 When and How to Withdraw Subjects

Reasons for treatment discontinuation include:

- Subject request or withdrawal of consent
- Subject non-compliance with the protocol
- Life-threatening or unacceptable adverse events at time of SRS or HBO treatment, such as HBO-induced seizure
- Physician judgment in view of subject's inter-current illness or safety considerations
- Administrative decision to discontinue the study.

3.4.2 Data Collection and Follow-up for Withdrawn Subjects

The date and reason for subject discontinuation from the study will be recorded. A discontinuation occurs when an enrolled subject ceases participation in the study, regardless of the circumstances. Withdrawal due to an adverse event will be distinguished from withdrawal from the study according to the definition of adverse event.

Despite the discontinuation, every effort will be made to complete the appropriate assessments. The patient will be followed using the standard follow-up procedures for patients who receive radiation therapy for brain metastases.

3.4.3 Replacement of withdrawn subjects

Patients withdrawn from the protocol as per Section 3.4.1 within one year of enrollment will not be deemed as counting towards the enrollment goal of twenty evaluable patients. Therefore, another patient (comparable in terms of resection status and tumor size) will be enrolled who may serve as a “substitute” for the withdrawn participant.

4 Study Intervention

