4.3 Acute HBO toxicity

We do not anticipate patients experiencing toxicities in conjunction with their HBO treatments. All will have undergone pre-screening for claustrophobia and barotrauma.

The likelihood of a seizure in conjunction with HBO treatment is less than one in a thousand (in the general population).

In the very unlikely event of a tonic-clonic seizure, the chamber will be brought to surface after air breaks and after tonic-clonic movements have subsided and regular respirations have resumed. Then the patient will be removed from the chamber and transported to the DHMC Emergency Department for further evaluation and management.

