6.1 Statistical Methods

For the primary outcome variable of feasibility, the twenty evaluable patients will be analyzed on the basis of the amount of time required from leaving the HBO chamber to beginning SRS for the target lesion (T1).

The goal for each patient (as discussed in Section 2.2) is for T1 to be no greater than 15 minutes. In a Phase I trial of HBO treatment in coordination with fully fractionated head-neck cancer XRT, DHMC established a track-record of an average of only eight minutes from time of leaving the HBO chamber to “beam on” for this patient group [22]. However, set-up for SRS treatment is more complex, involving placement of a head-frame and performance of a CT-scan prior to SRS treatment. These may extend the time interval required for patient set-up after leaving the HBO chamber.

We anticipate a learning curve for the team members of this study. Therefore, stopping rules are as outlined in Section 7.4: no more than 20% of first ten patients treated within

30 minutes of HBO; and no more than 33% of first fifteen patients treated within 30 minutes of HBO.

The primary endpoint of feasibility is defined as having been achieved if more than 50% of the 20 evaluable patients start SRS treatment within 30 minutes of leaving the HBO tank: in other words, T1 is ≤ 30 minutes for $>50\%$ of evaluable patients.

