6.3 Subject Population(s) for Analysis

The study population will be any subject enrolled in the study.

7 Safety and Adverse Events

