7.4 Stopping Rules

An internal stopping rule is set in place whereby the study will be terminated if (1) feasibility appears unattainable, or (2) a significant number of patients experience a significant adverse event (SAE) as outlined above:

- Regarding the primary endpoint of feasibility, we anticipate a steep learning curve for treatment of patients on this trial. The overall goal is to begin SRS within 15 minutes of exiting the HBO chamber; however, it is known that oxygen levels remain elevated in the brain up to 30 minutes after HBO treatment. The following stopping rules will be applied:
 - Analysis after enrollment of first 10 patients demonstrates no more than two patients (20%) treated within 30 minutes of HBO chamber exit.
 - Analysis after enrollment of first 15 evaluable patients demonstrates no more than five patients (33%) treated within 30 minutes of HBO chamber exit.
- Regarding the secondary endpoint of noninferiority, every patient who receives treatment on this protocol will be evaluated at every patient encounter for adverse events. Toxicities will be graded using the Common Toxicity Criteria Adverse Events (CTCAE) v4.0 of the National Cancer Institute.
 - Overall incidence of adverse events in this study will be reviewed every three months.
 - At time of any such review, if more than 40% of enrolled patients (minimum of 5 patients) experience SAEs that are deemed likely related to the protocol treatment (HBO combined with SRS), then the study will be terminated (i.e. more than 2 out of 5 patients, or more than 4 out of 10 patients, for example).
 - Note that some SAEs are expected in this patient population, given the nature of the disease process that is being treated. The stopping rule of 40% was elected as representing an incidence level significantly higher than that expected routinely in this patient population.
- It is the responsibility of the Principal Investigator to oversee the safety of the study. This safety monitoring will include careful assessment and appropriate reporting of adverse events as noted above, as well as quarterly review by the Norris Cotton Cancer Center Data and Safety Monitoring and Accrual Committee (see section 9 Auditing, Monitoring and Inspecting). Medical monitoring will include a regular assessment of the number and type of serious adverse events.

8 Data Handling and Record Keeping

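### Evaluable is never defined, and the one-year replacement rule in 3.4.3 can remove treatment-day failures and valid timings from a feasibility endpoint that is settled on the treatment day

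*Combined protocol and SAP*

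**What the plan says.** Section 6.1 declares feasibility if "more than 50% of the 20 evaluable patients start SRS treatment within 30 minutes of leaving the HBO tank". Section 4.2 has T1 timed by stopwatch on the treatment day.

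No section states what makes a patient evaluable. Section 3.4.3 comes closest: "Patients withdrawn from the protocol as per Section 3.4.1 within one year of enrollment will not be deemed as counting towards the enrollment goal". The target it refers to is 20 evaluable patients, and a substitute of similar resection status and tumor size is enrolled. The withdrawal reasons in Section 3.4.1 include "Life-threatening or unacceptable adverse events at time of SRS or HBO treatment, such as HBO-induced seizure", as well as patient request, non-compliance and physician judgment. Section 4.3 describes one route by which a treatment-day withdrawal could arise. After a seizure in the chamber, "Then the patient will be removed from the chamber and transported to the DHMC Emergency Department for further evaluation and management".

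The populations are described differently elsewhere:

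- Section 6.3: "The study population will be any subject enrolled in the study".
- Section 7.4, first feasibility look: "Analysis after enrollment of first 10 patients demonstrates no more than two patients (20%) treated within 30 minutes of HBO chamber exit".
- Section 7.4, second feasibility look: "Analysis after enrollment of first 15 evaluable patients demonstrates no more than five patients (33%) treated within 30 minutes of HBO chamber exit".
- Section 6.1 restates both looks, on ten and fifteen patients, without the word evaluable.

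**The concern.** A one-year criterion has a plausible purpose for recurrence, toxicity and survival. It does not suit an outcome settled within minutes of leaving the chamber. Applied to T1 it does two things.

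- It replaces a patient who is withdrawn on the treatment day without timely beam-on. That removes a failure from the denominator, so the shift always favors a pass.
- It discards the T1 of a patient who was timed normally and withdrew months later. That loses valid data, with no set direction.

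The plan also does not say how a patient with no T1 is scored. Read literally, evaluable status is not final until a year after enrollment, so the fifteen evaluable patients of the second look are not fixed when that look falls due.

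At stake is the primary objective, judged on 20 patients against a bare majority.

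**Working it through.** **The plan's own figures.** 2/10 = 20.0% and 5/15 = 33.3%, as Section 7.4 states. More than 50% of 20 means at least 11 (11/20 = 55%). The plan gives no significance level or power for feasibility.

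**How many replaced failures reverse a pass.** Let x be the successes among the 20 retained, and w the treated patients replaced after a same-day failure. The rate among all treated patients is x/(20 + w). It falls to 50% when w = 2x − 20.

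| Retained result | Replaced failures needed | Rate among all treated |
|---|---|---|
| 11/20 | 2 | 11/22 = 50% |
| 12/20 | 4 | 12/24 = 50% |
| 13/20 | 6 | 13/26 = 50% |
| 14/20 | 8 | 14/28 = 50% |

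The all-treated denominator is the one proposed here; no section states it. Under Section 6.3 the same 11/22 arises from any two withdrawn patients without timely beam-on, if a missing T1 is scored as a failure.

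**Chance of declaring feasibility.** Let p be the true rate of timely beam-on among all treated patients, and d the share of treated patients who are same-day failures and are replaced. Among those retained the success rate is p/(1 − d), so P(declare feasible) = P(X ≥ 11), with X binomial (20, p/(1 − d)).

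**Chance that the verdict changes.** This is the probability that X ≥ 11 and x/(20 + W) ≤ 0.5, where W, the number replaced before 20 are retained, is negative binomial.

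Inputs for d: Section 4.3 puts seizure with HBO below 1 in 1,000 in the general population, so d = 0.001 is taken as the documented level. The documents give no rate for all treatment-day withdrawals together; 1%, 5% and 10% are assumptions.

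| d | p/(1 − d) at p = 0.50 | P(declare feasible), p = 0.50 | P(verdict changes), p = 0.50 | P(verdict changes), p = 0.70 | P(verdict changes), p = 0.80 |
|---|---|---|---|---|---|
| 0 | 0.500 | 0.412 | 0 | 0 | 0 |
| 0.001 | 0.501 | 0.414 | 0.00003 | 0.00001 | <0.001 |
| 0.01 (assumed) | 0.505 | 0.430 | 0.003 | 0.001 | <0.001 |
| 0.05 (assumed) | 0.526 | 0.506 | 0.053 | 0.012 | <0.001 |
| 0.10 (assumed) | 0.556 | 0.611 | 0.149 | 0.019 | <0.001 |

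Including the two stopping looks changes the pass probabilities at p = 0.50 by no more than 0.001.

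**The second look.** P(stop) = P(X ≤ 5), with X binomial (15, p/(1 − d)). At p = 0.33 it is 0.629 for d = 0, 0.628 for 0.001, 0.573 for 0.05 and 0.510 for 0.10. A missed stop cannot rescue the trial: 5 of 15 plus five further successes is 10/20, which fails. The cost is at most five further evaluable patients.

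**The case against.** **It is an accrual rule.** Section 3.4.3 concerns an enrollment goal. It does not say that withdrawn patients' data leave the analysis, and Section 6.3 takes in everyone enrolled. This stands in part. A reader might infer that the protocol defines evaluable in 3.4.3 and orders failures deleted; it does neither. But 3.4.3 counts toward twenty evaluable patients and 6.1 analyzes twenty evaluable patients, so exclusion is the natural reading and nothing rules it out.

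**The event is rare.** The practice dive screens for ear equalization and claustrophobia beforehand, Section 4.3 anticipates no HBO toxicity, and Section 1.5 puts seizures at 0.06%. This stands as to size: the larger figures rest on assumed rates. However, seizure is only one of the reasons in 3.4.1, and its rate is for the general population.

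**A true rate of 50% is an unfavorable case.** Earlier fractionated treatment at the center averaged eight minutes. That stands too, although Section 6.1 itself warns that SRS set-up is more complex.

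**A medical event is not a coordination failure.** Scoring it as one is a choice, and treatment-related serious events have their own stopping rule in 7.4. That is a fair reason to report causes separately. It does not cover withdrawals after chamber exit that are not serious events, nor the discarded timings.

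**Conclusion.** The point holds as an undefined term combined with a replacement rule that does not fit a same-day endpoint, and with populations that differ between 3.4.3, 6.1, 6.3 and 7.4. It should be fixed, but its numerical weight is conditional. It can alter the result only close to the threshold, as when two replaced same-day failures turn 11/20 into 11/22. At the documented seizure rate it is negligible (0.412 to 0.414 at a true 50%). The range 0.430 to 0.611 depends on assumed same-day shares of 1% to 10%. At a true 80% the chance of a changed verdict is below 0.001 at every share examined.

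Three stronger inferences are not supported:

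- That slow patients are replaced. Late beam-on alone is not a withdrawal reason, so such a patient remains a counted failure.
- That a false claim of feasibility is likely. The documents give no overall same-day withdrawal rate from which to conclude this.
- That the matched-control comparison is materially biased. Replacement could affect it, but the documents give no basis for a size.

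**What to change.** For the primary endpoint and both feasibility looks, define a separate feasibility set: every patient who starts treatment-day HBO, irrespective of later withdrawal.

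- **Success:** the patient completes the HBO session as the protocol specifies it and has beam-on within 30 minutes of chamber exit. Requiring completion prevents a shortened session followed by prompt SRS from counting as a success.
- **Failure:** all others, including those with no T1 or an incomplete session. Report the reasons, so that medical events can be told apart from logistical delay.
- **Replacement:** for this endpoint, only before treatment-day HBO starts (for example, a patient lost at the practice dive), with numbers and reasons reported.
- **One-year rule:** limit 3.4.3 to accrual for follow-up outcomes.
- **Alignment:** use the same set in 3.4.3, 6.1, 6.3 and both looks in 7.4.

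As a precaution only, keep all treated patients in the secondary analyses, using the follow-up after discontinuation in 3.4.2 where consent and authorization permit; after a revocation, 8.1 allows use only of data already collected.

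The cost is wording. There are no added visits and no change to patient management. The reported feasibility rate may be slightly lower.

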For the secondary endpoints, using Cox proportional hazards models, and Kaplan-Meier survival statistics, the overall group of 20 will be analyzed for event-free survival and compared against a matched set of patients from our institution (see below for methodology). This match will be based on tumor size, resection status, and histology-specific graded prognostic assessment (GPA). The GPA is a validated, widely accepted prognostic scale predictive of survival for patients presenting with brain metastases. Diagnosis-specific GPA calculation is based on published criteria including tumor histology, presence of systemic metastases, number of brain metastases, age, performance status, and breast-cancer specific molecular markers [29-31]. Further demographic and treatment data will also be collected, including: gender, subtotal resection versus gross total resection (if tumor resected), tumor diameter (prior to first treatment, whether surgery or SRS), SRS target volume (PTV), and prescribed dose to the PTV. The secondary outcome variables will be the first occurrence of the event of interest and also the time until the first occurrence of the event of interest. These events include: intracranial recurrence at SRS site, intracranial recurrence at a distant site, whole brain XRT, second SRS (classified as either local or distant), third SRS (classified as local or distant), radionecrosis at the SRS site, and death.

A retrospective database pertaining to Dartmouth-Hitchcock's experience with stereotactic radiosurgery in the treatment of brain metastases is being collected through Study 00030625 (PI [name]). Pertinent matching variables, along with demographic variables, treatment variables, and outcome variables for the control population are available on 00030625. The matching variables (histology, lesion size, resection status, and calculated GPA) will be used to identify a control population in the Study 00030625 that match 1:1 against the D12129 enrolled patient population.

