Specifically, patients with similar tumor histologies will be matched against histologies found in the D12129 patient population, falling into one of six categories: (1) non-small cell lung cancer, (2) melanoma, (3) breast cancer, (4) renal cell cancer, (5) GI cancers, and (5) other histologies. Once a histologic match is identified, the patient is then matched by resection status (either unresected or resected). The third matching variable is then GPA. If an exact GPA match is not available in the 000030625 data base, then a patient with a higher GPA will be selected, with the control patient's GPA as near as possible to that of the corresponding D12129 patient (thereby, if anything, biasing the survival outcome data slightly against the D12129 data set). Lastly, the fourth matching variable is tumor size (i.e. maximum tumor diameter) at time of treatment (a categorical variable, either below or above 2.0 cm). If an exact match for the fourth variable is not available in the 000030625 data base, then size will be matched as closely as possible to the 2.0 cm cut-off from those patients available in this historical database. These

matching patients identified in 000030625 data base will serve as the control group for the D12129 study.

Once the control group patients have been selected, their data will be extracted from the 000030625 database in de-identified form. These data will be reviewed by an “honest broker” to assure proper de-identification and HIPAA compliance. These de-identified control group data will then be merged with the D12129 dataset. Analysis of this combined data base then will allow comparison of HBO-treated and control patients in terms of event-specific outcome parameters, with events including: death, local intracranial recurrence, distant intracranial recurrence, whole brain radiation therapy, and repeat SRS (either local or distant).

Exploratory variables will include QOL data and tumor markers. Comparisons for change in markers before versus after HBO-SRS treatment will be performed for the entire group of twenty patients. Also comparisons will be performed for subgroups (including comparisons of those with resections versus those without, and of those above 2.0 cm diameter versus those below).

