6.2 Sample Size Determination

For the initial phase of this study we anticipate enrolling 20 patients (DHMC treats about 80-100 SRS patients yearly): 5 with resected lesions up to 2.0 cm (diameter), 5 with intact lesions up to 2.0 cm, 5 with resected lesions greater than 2.0 cm, and 5 with intact lesions greater than 2.0 cm. Based on a median event-free survival time of 6 months in the control group, a log-rank test with a one-sided significance level of 0.05 and a power of 0.80 can detect a relative risk of 0.39 or smaller. Thus, we have sufficient power to detect 61% increase in the risk of toxicity, recurrence or death.

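### The plan does not settle whether patients withdrawn and replaced within a year stay in the comparison with historical controls; if they are left out, survival and recurrence may be biased

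*Combined protocol and SAP*

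**What the plan says.** Section 3.4.3: "Patients withdrawn from the protocol as per Section 3.4.1 within one year of enrollment will not be deemed as counting towards the enrollment goal"; the goal is 20. A substitute of similar resection status and tumour size is enrolled instead.

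Section 3.4.1 lists five reasons: subject request or withdrawn consent; non-compliance; severe adverse events, limited to those at the SRS or HBO treatment; "Physician judgment in view of subject's inter-current illness or safety considerations"; and an administrative decision to stop the study. Death and recurrence are not on the list.

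Section 3.4.2 keeps withdrawn patients under observation: "Despite the discontinuation, every effort will be made to complete the appropriate assessments".

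Section 6.1, secondary endpoints: "the overall group of 20 will be analyzed for event-free survival and compared against a matched set of patients from our institution". Controls are chosen from a retrospective database on histology, resection status, GPA and tumour size. No rule removes a control because of later events. The same section says that the controls are to "match 1:1 against the D12129 enrolled patient population".

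Section 6.3: "The study population will be any subject enrolled in the study".

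**The concern.** HBO with SRS is given once, so nearly all of the one-year replacement window lies after treatment. If the 20 in section 6.1 are the patients left after replacement, a patient belongs to the HBO group only if not withdrawn during the following year. Controls enter on baseline features alone and keep whatever outcome they had. That is selection on post-treatment events in one arm.

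The secondary objective is non-inferiority to these controls. A rule that changes the apparent event rate in the HBO group alone can move that conclusion either way. Because sections 3.4.3 and 6.1 support one analysis set and section 6.3 another, the choice could also be made after outcomes are known.

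**Working it through.** **1. The plan's own figure.** Section 6.2 states that "a log-rank test with a one-sided significance level of 0.05 and a power of 0.80 can detect a relative risk of 0.39 or smaller", with a control median of 6 months. With 20 per group and exponential times, Freedman's formula gives (1.645 + 0.842)² × [(1 + 0.39)/(1 − 0.39)]² = 6.18 × 5.19 = 32.1, so 33 events. With 24 months of follow-up each (section 5.4), expected events are 20(1 − 1/16) + 20(1 − 2^(−1.56)) = 18.75 + 13.2 = 32.0, giving power 0.799 and a detectable ratio of 0.389. With 36 months of accrual plus a 12-month minimum (section 6.1), expected events are 33.1 and the detectable ratio is 0.397. The figure therefore reproduces as 20 against 20. It does not tell us which 20.

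**2. Which set the text supports.**

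| Text | Set implied once someone is replaced |
|---|---|
| 3.4.3 with the group of 20 in 6.1 | the 20 left after replacement |
| 6.1, matching sentence | all enrolled |
| 6.3 | all enrolled |
| 3.4.2 | none stated, but outcomes of withdrawn patients are collected |

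**3. Direction.** Let S be true one-year survival. Let p_d be the fraction withdrawn among those who would die within the year, and p_s the fraction among those who would survive it. Apparent survival after replacement is

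S(1 − p_s) / [S(1 − p_s) + (1 − S)(1 − p_d)].

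This exceeds S only when p_d > p_s.

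**4. Size.** S = 0.525 comes from Table 1 in section 1.1, a resected series; section 6.2 plans half the patients with intact lesions. All withdrawal rates are assumptions.

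*Withdrawal precedes decline (p_s = 0):*
- p_d = 10%: 0.525/(1 − 0.0475) = 55.1%, with 20/0.9525 = 21.0 enrolled to reach 20
- p_d = 20%: 0.525/0.905 = 58.0%, 22.1 enrolled
- p_d = 30%: 0.525/0.8575 = 61.2%, 23.3 enrolled

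The same formula applied to freedom from local recurrence (85.5% in Table 1), withdrawing 10% to 30% of those who would recur, gives 86.8% to 89.4%.

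*Withdrawal unrelated to prognosis (constant hazards).* Let p be the probability of withdrawal by 12 months, a = −ln 0.525 = 0.644 and b = −ln(1 − p). Retained survivors are S(1 − p). Retained deaths are [a/(a + b)] × [1 − S(1 − p)].
- p = 10%: survivors 0.4725, deaths 0.8595 × 0.5275 = 0.4534, apparent survival 0.4725/0.9259 = 51.0%
- p = 30%: survivors 0.3675, deaths 0.6437 × 0.6325 = 0.4071, apparent survival 0.3675/0.7746 = 47.4%

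Here p_s > p_d, because a patient who dies early has had less time in which to be withdrawn.

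**5. Effect on the log-rank comparison.** Simulation: event-free survival, no true effect, 20 against 20, control median 6 months, 36 months of accrual plus 12, 30,000 runs per row.

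| Scenario | Median apparent HR | One-sided 0.05 test favours HBO |
|---|---|---|
| All enrolled kept | 1.00 | 0.053 |
| 10% of those with an event within 12 months withdrawn first | 0.96 | 0.071 |
| 20% | 0.92 | 0.092 |
| 30% | 0.87 | 0.117 |
| Unrelated withdrawal, 10% by 12 months | 1.04 | 0.044 |
| Unrelated withdrawal, 30% | 1.12 | 0.025 |

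**The case against.** The strongest reply is that section 3.4.3 governs only the enrolment count and nowhere deletes outcomes. Section 6.1 uses the word evaluable for the primary endpoint but not for the secondary one, so its group of 20 may just be the planned number, as distinct from the resection and size subgroups. Sections 6.3 and 3.4.2 fit that reading. This stands: removal from the secondary comparison is a plausible reading, not an established fact. What it does not do is resolve the conflict, since 6.3 does not mention replacement.

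A reader might infer more: that the rule takes out failing patients and so biases the comparison in favour of HBO. The documents do not support that as a certainty.
- The adverse-event reason is confined to the treatment session, so late toxicity such as radionecrosis does not fall under it.
- Hospice entry, death and recurrence are not withdrawal reasons. A patient who declines and dies without being formally withdrawn stays in.
- Subject request, non-compliance and physician judgment can precede decline, but need not.
- Large effects need extreme assumptions. Withdrawing 50% of those who would die gives 69% apparent survival, but means 0.5 × 0.475 = about 24% of all enrolled patients withdrawn, every one a future death.

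Nor can one say that the rule cancels the conservative GPA fallback, which section 6.1 describes as "thereby, if anything, biasing the survival outcome data slightly against the D12129 data set". Neither effect can be quantified from the documents, so the net direction is unknown.

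**Conclusion.** The concern holds as an unresolved analysis set with a conditional bias. Sections 3.4.3 and 6.1 can be read as excluding withdrawn patients; section 6.3 and the matching sentence in 6.1 include them. On the first reading, HBO-group membership depends on post-treatment events in one arm only.

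Under the assumed 10% to 30% rates, the distortion in one-year survival runs from +2.6 to +8.7 points if only patients heading for death are withdrawn, and from −1.5 to −5.1 points if withdrawal is unrelated to prognosis. A bias toward HBO is the more plausible direction if illness, safety or non-compliance withdrawals precede decline, but it is not certain. These sizes rest on the resected-series survival, no true effect and assumed withdrawal rates. The plan gives no non-inferiority margin, so the effect on that conclusion cannot be computed. Keeping every treated patient removes both distortions, whichever applies.

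**What to change.** Reconcile sections 3.4.3, 6.1 and 6.3:
- State in 3.4.3 that replacement affects only the enrolment and feasibility count.
- In 6.1 and 6.3, define the secondary population as every patient who started the treatment-day HBO session, replaced or not, each with a matched control. This replaces the reference to a group of 20. It also settles the position of enrolled patients who never reached treatment, whom 6.3 as worded would include.
- Run time from SRS in both groups, use the outcomes collected under 3.4.2, and censor only at last follow-up or withdrawal of consent to data use.
- Report the 20-evaluable set as a sensitivity analysis.

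The cost is wording plus one matched control per replaced patient from the existing database. No new visits are needed, because 3.4.2 already follows these patients. The HBO results may come out less favourable.
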